2. INTRODUCTION

This SAP provides the detailed methodology for summary and statistical analyses of the data collected in Study C1071009. This document may modify the plans outlined in the protocol; however, any major modifications of the primary endpoint definition or its analysis will also be reflected in a protocol amendment.

Any deviations from this analysis plan will be described in the CSR.

Study C1071009 is a prospective, open-label, multicenter, non-randomized Phase 1/2 study aimed to evaluate the safety (in particular the rate of Grade ≥ 2 CRS) of a priming dose regimen that involves premedication and 2 step-up priming doses to be administered within the first week of elranatamab treatment in RRMM participants who are refractory to at least 1 PI, 1 IMiD, and 1 anti-CD38 mAb. There is one planned interim analysis for futility, which takes place once 30 participants in Part 1 either complete Cycle 1 of study intervention or discontinued the study intervention prior to the end of Cycle 1. The primary analysis will be conducted once all participants have completed Cycle 1 of study intervention or have otherwise discontinued the study intervention. All summaries and analyses will include all data pertaining to visits/assessments performed up to and including the data cutoff date.

2.1. Study Objectives, Endpoints, and Estimands

Type	Objectives	Endpoints	Estimands
Primary			
Safety	
 To assess the rate of Grade ≥ 2 CRS when elranatamab is administered with a dosing regimen of 2 step-up priming doses and premedication in participants with RRMM. 	
 Grade ≥ 2 CRS rate during C1. 	
 The primary estimand is rate of Grade ≥ 2 CRS during C1 as assessed by ASTCT criteria. It will be estimated based on all enrolled RRMM participants who received at least 1 dose of study intervention regardless of duration on the study treatment.
Secondary			
Safety	
 To assess the safety and tolerability of elranatamab at doses >76 mg with a longer dosing interval (>1 week) in order to identify the RP2D (Part 2A only). 	
 Incidence of DLTs during DLT observation period 	
 The secondary estimand is DLT rate estimate based on data from DLT-evaluable participants during the DLT observation period.

Type	Objectives	Endpoints	Estimands
Safety	
 To evaluate the overall safety profile of elranatamab with 2 step-up priming doses and alternative dosing regimens in participants with RRMM. 	
 Adverse Events as characterized by type, frequency, severity as graded by NCI CTCAE version 5.0, timing, seriousness, and relationship to elranatamab. The severity of CRS and ICANS will be assessed according to ASTCT criteria; Laboratory abnormalities as characterized by type, frequency, severity (as graded by NCI CTCAE version 5.0), and timing. 	
 Not Applicable.
Efficacy	
 To evaluate the anti-myeloma activity of elranatamab with alternative dosing regimens in participants with RRMM. 	
 ORR and CRR, per IMWG response criteria as determined by investigator; Time to event endpoints: TTR, DOR, DOCR and PFS per IMWG response criteria as determined by investigator, and OS; MRD (assessed by central lab) negativity rate per IMWG sequencing criteria. 	
 Not Applicable.
PK	
 To evaluate the PK of elranatamab 	
 Pre- and postdose concentrations of elranatamab. 	
 Not Applicable.
Immunogenicity	
 To evaluate immunogenicity of elranatamab 	
 Incidence and titers of ADA and NAb against elranatamab. 	
 Not Applicable.
CCI			
[REDACTED]	[REDACTED]	[REDACTED]	[REDACTED]

Type	Objectives	Endpoints	Estimands
CCI	[REDACTED]	[REDACTED]	[REDACTED]
	[REDACTED]	[REDACTED]	[REDACTED]
	[REDACTED]	[REDACTED]	[REDACTED]

2.2. Study Design

Study C1071009 is a prospective, open-label, multicenter, non-randomized Phase 1/2 study aimed to evaluate the safety (in particular the rate of Grade ≥ 2 CRS) of a priming dose regimen that involves premedication and 2 step-up priming doses to be administered within the first week of elranatamab treatment in RRMM participants who are refractory to at least 1 PI, 1 IMiD, and 1 anti-CD38 mAb. All participants in all dosing groups will contribute to the primary objective of the study, ie, assessing the rate of Grade ≥ 2 CRS during C1, as the same dosing regimen is administered to all treatment groups during the first cycle.

For both Part 1 and Part 2, the first 2 doses of elranatamab on C1D1 and C1D4 will serve as the step-up priming doses and will be administered on an inpatient basis to monitor participants for CRS/ICANS. The dose of elranatamab should be increased to 20 and 76 mg on C1D4 and C1D8, respectively, as long as the participant meets redosing criteria as specified in [Section 6.5.1](#) of the protocol.

In addition, the study will evaluate the overall safety, tolerability, PK, pharmacodynamics, and preliminary anti-myeloma activity of alternative regimens of elranatamab at dose levels >76 mg starting from Cycle 2 with different dosing intervals (QW, Q2W, Q4W) (Part 2), and a regimen of elranatamab full dose of 76 mg QW for 6 cycles followed by Q2W or >76 mg Q4W (Part 1).

The following dosing regimens will be assessed:

- **Part 1: Premedication, 2 step-up priming doses, and full dose 76 mg QW for 6 cycles followed by Q2W and/or RP2D (116 mg or 152 mg) Q4W;**

Part 1 aims to evaluate the overall safety, tolerability, PK, pharmacodynamics, and preliminary anti-myeloma activity of the following regimen:

- **C2 to C6:** elranatamab 76 mg QW;
- **C7 onwards:** elranatamab 76 mg Q2W (for participants with IMWG response of PR or better persisting for ≥ 2 months on QW).

If after switching to Q2W interval, the participant subsequently begins to have an increase of disease burden not yet qualifying as PD according to IMWG criteria, dose intervals should return to 76 mg QW for the remainder of the study.

- **C7 onwards once the RP2D is identified in Part 2A:** elranatamab RP2D (116 mg or 152 mg) Q4W (for participants with IMWG response of PR or better persisting for ≥ 2 months on QW or Q2W).

If after switching to Q4W interval; the participant subsequently begins to have an increase of disease burden not yet qualifying as PD according to IMWG criteria, dose intervals should return to RP2D (116 mg or 152 mg) Q2W for the remainder of the study.

- **Part 2: Premedication, 2 step-up priming doses, and full dose >76 mg (ie 116 and 152 mg) at different dosing intervals.**

Part 2 aims to evaluate the safety and efficacy of a regimen that includes premedication and a dosing regimen of 2 step-up priming doses (Week 1) followed by full dose >76 mg with different dosing intervals starting from C2. Part 2 includes a dose determination part (Part 2A Dose level 1 and Dose level 2), a dose expansion part (Part 2B), **CCI** Part 2A dose determination and Part 2C tolerability evaluation will be based on a BLRM approach. The decision to start enrolling participants in a new cohort (Part 2A Dose level 2, Part 2B or Part 2C) will be a joint decision to be determined by the investigators and the sponsor in dose level review meetings.

- **Part 2A** will evaluate full elranatamab doses >76 mg starting from C2 with a longer dosing interval (>1 week) to determine the potential RP2D to be further evaluated in Part 2B. Approximately 8 participants will be enrolled at each dose level in Part 2A. The potential RP2D identified in Part 2A Dose Level 1 or Dose Level 2 will be further evaluated and confirmed in Part 2B (dose expansion).
- **Part 2B** will begin once the potential RP2D from Part 2A Dose level 1 or Dose level 2 is selected. Approximately 22 participants will be enrolled to confirm the safety and efficacy of the selected dosing regimen. Approximately a total of 30 participants will be enrolled and treated at the potential RP2D, 8 from Part 2A and 22 from Part 2B.

[figure not shown]
[figure not shown]

Figure 1. Study Design

3. ENDPOINTS AND BASELINE VARIABLES: DEFINITIONS AND CONVENTIONS

3.1. Primary Endpoints

The primary endpoint is Grade ≥ 2 CRS rate during Cycle 1, defined as the proportion of participants in the Safety Analysis Set experiencing Grade ≥ 2 CRS as assessed by ASTCT¹ criteria.

3.2. Secondary Endpoints

3.2.1. Efficacy Endpoints

3.2.1.1. Objective Response Rate

Objective response rate (ORR) is defined as the proportion of participants in the Safety Analysis Set with an objective response per the IMWG response criteria² as determined by investigator.

Objective response is defined as having a best overall response (BOR) of confirmed stringent complete response (sCR), complete response (CR), very good partial response (VGPR) or partial response (PR) per IMWG response criteria.

For all efficacy endpoints per IMWG response criteria, BOR will be assessed programmatically based on investigator reported overall responses recorded at evaluation time points from the date of first dose until confirmed progressive disease (PD), withdrawal of consent, participant lost to follow-up, death or start of new anti-cancer therapy or defined end of study, whichever occurs first.

3.2.1.2. Complete Response Rate

Complete response rate (CRR) is defined as the proportion of participants with a BOR of confirmed sCR or CR per IMWG criteria as determined by investigator.

3.2.1.3. Duration of Response

Duration of response (DOR) is defined, for participants with an objective response per IMWG criteria as determined by investigator, as the time from the first documentation of objective response that is subsequently confirmed, until confirmed PD per IMWG criteria, or death due to any cause, whichever occurs first.

3.2.1.4. Duration of Complete Response

Duration of complete response (DOCR) is defined, for participants with a BOR of confirmed sCR or CR per IMWG criteria as determined by investigator, as the time from the first documentation of sCR or CR that is subsequently confirmed, until confirmed PD per IMWG criteria, or death due to any cause, whichever occurs first.

3.2.1.5. Progression-free Survival

Progression-free survival (PFS) is defined as the time from the date of first dose until confirmed PD per IMWG criteria as determined by investigator, or death due to any cause, whichever occurs first.

3.2.1.6. Overall Survival

Overall survival (OS) is defined as the time from the date of first dose until death due to any cause.

3.2.1.7. Time to Response

Time to response (TTR) is defined, for participants with an objective response per IMWG criteria as determined by investigator, as the time from the date of first dose to the first documentation of objective response that is subsequently confirmed.

3.2.1.8. Minimal Residual Disease Negativity Rate

Minimal Residual Disease (MRD) (assessed by central lab) negativity rate is the proportion of participants with negative MRD per IMWG sequencing criteria from the date of first dose until confirmed PD, withdrawal of consent, participant lost to follow-up, death or start of new anticancer therapy or defined end of study, whichever occurs first.

3.2.2. Safety Endpoints

3.2.2.1. DLT Rate (Part 2A and Part 2C only)

Dose limiting toxicity (DLT) rate is defined as the number of DLT-evaluable participants with DLTs in the DLT observation period divided by the number of DLT-evaluable participants in the DLT observation period. DLT observation period is Cycle 2 or 28 days starting from the first dose of 116 mg or 152 mg.

3.2.2.2. Adverse Events and Laboratory Parameters

- Adverse Events (AEs) and laboratory abnormalities as graded by the National Cancer Institute Common Terminology Criteria for Adverse Events (NCI CTCAE) version 5.0.
- Cytokine release syndrome (CRS), immune cell-associated neurotoxicity syndrome (ICANS) graded according to ASTCT criteria.¹

3.2.3. Pharmacokinetic Endpoints

- Pre- and post-dose concentrations of elranatamab.

3.2.4. Immunogenicity Endpoints

- ADAs and Nabs against elranatamab.

CCI [REDACTED]

[REDACTED]

[REDACTED]

[REDACTED]

[REDACTED]

[REDACTED]

[REDACTED]

[REDACTED]

[REDACTED]

CCI

[REDACTED]

3.4. Baseline Variables

Start and end dates of study intervention:

The date of first dose (start date) of study intervention is the earliest date of nonzero dosing of the study drug.

The date of last dose of study intervention is the latest date of the nonzero dosing of the study drug.

Definition of baseline:

No windowing will be applied when defining baseline. For example, the protocol requires safety assessments to be performed within 28 days prior to first dose; however, values outside this window will not be excluded when determining baseline assessments. Any deviations from the protocol specified window will be documented as protocol deviations. A separate definition of adequate baseline ([Section 5.2.9](#)) is provided for disease assessment related efficacy endpoints.

For all endpoints, the last assessment performed on or prior to the date of the first dose of study intervention will serve as the baseline assessment. If there are no observations meeting these criteria, then baseline is considered missing.

Participants who start treatment and discontinue from the study on the same day may have 2 different sets of data collected on Study Day 1 (one during study and one in the End of Treatment [EOT] visit). Data reported at the EOT visit are not eligible for baseline selection.

Triplicate ECGs are collected at all timepoints except screening (single ECG at screening); therefore, the baseline for ECG measurement is the pre-dose on Cycle 1 Day 1, or the most recent ECG assessment reported prior to the first administration of study drug. Unscheduled assessments will not be included in the calculation of the average. The average of the replicate measurements will be determined after the derivation of the individual parameters at each timepoint.

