### 2.3.1. Risk Assessment

Potential Risk of Clinical Significance	Summary of Data/Rationale for Risk	Mitigation Strategy
Study Intervention: Elranatamab monotherapy		

CRS
	
A known toxicity of therapeutics that function by activation of immune effector cells.
 
Circulating cytokines are elevated after IV or SC administration of elranatamab. CRS signs and symptoms are expected mainly after the first and second dose and occasionally after the third or later doses of elranatamab.
 
In the present study, elranatamab dose will be increased to > 76 mg starting from Cycle 2 either with longer dosing intervals in Part 2A DLI, Part 2A DL2, and Part 2B CCI [REDACTED]
 
For Part 2, the planned regimen would result in up to 2-fold higher Cmax on Cycle 2 Day 1 (152 mg Q2W) compared to 76 mg QW. Higher Cmax during the first 24 hours of the first
	
Participants will be hospitalized for at least 2 days after the CID1 dose and at least 1 day after the CID4 dose for safety surveillance (Part 1, Part 2). Hospitalization from CID1 to CID5 may be considered. Since CRS events occurred after the first (predominantly within the first 2 days) and second dose of eh-anatamab, the planned 2-day hospitalization after the first dose allows for the detection of initial CRS signs and symptoms and enables timely management of these events according to the ASTCT management guidelines. The 1-day hospitalization on CID4 is considered adequate given the anticipated lower incidence and grade CRS after the second step-up dose of 20 mg.
 
For Part 2A, participants will be hospitalized for at least 1 day also on C2D1. For Part 2B and Part 2C, hospitalization on C2D1 may not be required depending on CRS profile observed in Part 2A. For participants enrolled in Part 1 who would switch to the RP2D Q4W, optional hospitalization may be considered on the day of RP2D administration depending on CRS profile observed in Part 2A and Part 2B.
 
The 2 step-up priming doses schema is expected to mitigate the rate and severity of CRS, which is mainly expected after the first 1 to 2 doses.
 
To further mitigate the CRS risk, premedications will be administered prior to the first 3 doses on CID1, CID4 and CID8 (see Section 6.8.I). No premedications will be administered on C2D1 for Part 2 as the risk of CRS after repeated eh-anatamab administration, even with a higher eh-anatamab dose, is considered low.
 
Guidance for monitoring, grading, and management of CRS per ASTCT criteria and guidelines is included in Appendix 12.
 
Dose modification/discontinuation in the setting of Grade 2 AEs (including CRS) is described in Section 6.5.
 
This study will include only participants who are likely to tolerate potential events of CRS by excluding participants who are particularly susceptible to complications of CRS, including those with impaired cardiac function or clinically significant CV disease (see Section 5.1 and Section 5.2).
 
Criteria for temporary study hold based on Grade 3 CRS events are described in Section 9.4.1.

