3.5. Safety Endpoints

Safety endpoints will be summarized based on the on-treatment period unless otherwise specified.

The on-treatment period is defined as the time from the first dose of study intervention through the minimum of 90 days after last dose, or (start day of new anticancer therapy - 1 day). Anticancer therapy includes drug therapy and radiation with curative intent; the start of new anticancer therapy after the first dose of study intervention is derived as outlined in [Section 5.2.6](#). Adverse events occurring on the same day as the first dose of study intervention will be considered to have occurred during the on-treatment period. All other assessments which occur on the same day as the first dose of study intervention will be considered baseline assessments (see [Section 3.4](#) for the definition of baseline).

Safety data collected after the on-treatment period as described above will be listed but not summarized.

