5.2.11. Nominal and Unscheduled Visits

For all algorithms and analyses, visit labels as specified on the CRF will be used as the nominal timepoint (ie, assessment will not be slotted).

Unless otherwise specified, unscheduled assessments will not be displayed in summary tables by nominal visit/timepoint. Unscheduled assessments will be used when deriving baseline and worst case on-treatment for safety analyses (except where noted for baseline ECGs). Additionally, unscheduled assessments will be used for efficacy analyses (eg, defining date of progression/censoring, best overall response, date of last contact).

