6.8.3. Laboratory Data

Laboratory results will be converted to International System of Units (Système International d'unités, SI) units which will be used for applying toxicity grades and for all summaries.

As described in [Section 3.4](#), baseline will be defined as the last assessment performed on or prior to date of the first dose of study intervention. If there are multiple assessments that meet the baseline definition on the same day without the ability to determine which was truly last, then the worst grade will be assigned as the baseline grade.

Results collected as strict inequalities (eg, >10 , <10) will be converted to numeric values adding or subtracting a factor of $<0.001>$. Expressions of the form “ \geq ” or “ \leq ” will be converted to the end point. These numeric values will be evaluated for clinically significant abnormalities, but will not be included in calculations of summary statistics except for efficacy related laboratory results. Additional data handling rules for efficacy related laboratory data will be described in the programming plan.

Additionally, laboratory results will be programmatically classified according to NCI-CTCAE version 5.0 grade. Non-numerical qualifiers will not be taken into consideration in the derivation of grade (eg, hypokalemia Grade 1 and Grade 2 are only distinguished by a non-numerical qualifier and therefore Grade 2 will not be derived). In summary statistics the number and percentage of participants corresponding to grades that only include non-quantitative criteria will be displayed as a blank or NA (not assessed) rather than 0. If there is any overlap between grade criteria (eg, CTCAE grading criteria for Creatinine Increased – a value can fall into one range based on comparison to Upper Limit of Normal (ULN) and another range based on comparison to baseline), the highest (worst) grade would be assigned to that record. Grade 5 is defined in the CTCAE criteria guidance as an event with an outcome of death. Since laboratory data does not collect an outcome, Grade 5 is not used when programmatically grading laboratory data.

For laboratory tests without CTCAE grade definitions, results will be categorized as normal, abnormal, or not done.

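### Laboratory baseline is set by the date, not the time, of first dose, so an unscheduled sample drawn after dosing on Day 1 becomes the baseline and can understate laboratory shifts

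*SAP*

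**What the plan says.** Four SAP rules act together on laboratory baseline.

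- SAP 3.4, whatever the endpoint: "the last assessment performed on or prior to the date of the first dose of study intervention will serve as the baseline assessment".
- SAP 3.5, having classed Day 1 adverse events as on-treatment: "All other assessments which occur on the same day as the first dose of study intervention will be considered baseline assessments".
- SAP 5.2.11: "Unscheduled assessments will be used when deriving baseline and worst case on-treatment for safety analyses", with an exception for baseline ECGs.
- SAP 6.8.3 repeats the date rule for laboratory data. Where several same-day values qualify "without the ability to determine which was truly last, then the worst grade will be assigned as the baseline grade".

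Two provisions in SAP 3.4 are stricter. ECG baseline is the C1D1 pre-dose record or "the most recent ECG assessment reported prior to the first administration of study drug". End-of-treatment data collected on Study Day 1 may not be used as baseline.

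The protocol governs when samples are taken. The Schedule of Activities requires treatment-period assessments (disease assessments excepted) within 72 hours before dosing. Protocol 8.2.6 requires laboratory reports to be reviewed before dosing on dosing days, and also permits unscheduled laboratory tests at any time for a perceived safety issue.

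**The concern.** A baseline should describe the participant before exposure. Under these rules a laboratory value affected by the first 4 mg dose can become the reference against which later values are judged. It is then lost twice: it raises the baseline grade, and it drops out of the post-baseline maximum.

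Such a draw is plausible here. Participants stay in hospital for at least 2 days after C1D1, and Protocol 2.3.1 reports that CRS after the first dose arose "predominantly within the first 2 days". The protocol also expects relevant laboratory changes: Table 6 treats lymphopenia as a consequence of the mechanism, and Table 5 gives Grade 3 transaminitis as an example of an event attributed to CRS. Repeat samples would tend to come from participants who were unwell, so any error would be selective.

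The outputs at stake are:

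- the laboratory shift tables in SAP 6.8.3, including the one from Grade 2 or lower to Grade 3 or higher;
- the liver-test categories and post-baseline liver listings in the same section;
- the exploratory subgroups by baseline liver and renal function in SAP 6.6. There, an AST or creatinine change accompanying CRS could decide the subgroup in which that participant's CRS outcome is counted.

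**Working it through.** The plan states no figure on this point, so the check follows the rules through.

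**Step 1. Which samples are exposed?** The scheduled C1D1 hematology and chemistry are pre-dose (Schedule of Activities; Protocol 8.2.6). The next scheduled safety sample is hematology on Day 4. Samples from Day 2 onward are post-baseline under either a date rule or a date-and-time rule. The exposed set is therefore unscheduled or off-protocol samples taken between the first dose and the end of that calendar day.

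**Step 2. Does any SAP rule protect the pre-dose value?** No. If collection order is known, the later (post-dose) value is the last one on that date and is selected. If order is unknown, the worse grade is selected. Within-day order is used where available; dosing time is not. SAP 3.5 is also at odds with itself: it starts the on-treatment period at the first dose, then assigns every same-day laboratory value to baseline.

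**Step 3. Effect on the shift tables.** The grades below are illustrative.

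| Case | Pre-dose | Post-dose Day 1 | Day 2 | SAP: baseline to worst post-baseline | Date-and-time rule |
|---|---|---|---|---|---|
| (a) No post-dose draw | 0 | none | 1 | 0 to 1 | 0 to 1 |
| (b) Worsens, then recovers | 0 | 3 | 1 | 3 to 1 | 0 to 3 |
| (c) Worsens and persists | 0 | 3 | 3 | 3 to 3 | 0 to 3 |
| (d) As (b), order unknown | 0 | 3 | 1 | 3 to 1 | 0 to 3 |

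In (a) nothing changes. In (b) and (d) the Grade 3 value disappears from the post-baseline maximum. In (c) Grade 3 still appears as the worst post-baseline grade, but not as a shift. In (b), (c) and (d) the participant is missing from the table of shifts from Grade 2 or lower to Grade 3 or higher. A post-dose draw with an unchanged grade leaves the baseline grade as it was. A draw that improved, with known order, would err in the other direction.

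**Step 4. Other outputs.** The liver-test categories count values in the on-treatment period, and the liver listings select post-baseline elevations. Read with the same-day sentence in SAP 3.5, a post-dose Day 1 elevation counts in neither. For the liver subgroup no grade change is needed: AST or bilirubin moving above the upper limit of normal is enough.

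**Step 5. Size.** The documents give no frequency of post-dose Day 1 draws. As a pure assumption, 5% to 50% of the planned 76 participants would give 0.05 × 76 = 3.8 to 0.50 × 76 = 38 exposed baselines. These are not masked shifts. Masking also requires the value to worsen within that calendar day, so the number of masked shifts is smaller.

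**The case against.** The strongest reply is that this is a narrow gap in descriptive tables. Much of it stands.

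- A reader might infer that Day 1 laboratory values in general become a contaminated baseline. The documents do not support that: scheduled Day 1 samples are pre-dose.
- A reader might infer that early toxicity is hidden from the study. That does not follow either. SAP 3.5 says "Adverse events occurring on the same day as the first dose of study intervention will be considered to have occurred during the on-treatment period", Protocol 8.2.6 requires clinically relevant laboratory changes to be recorded as adverse events, and all laboratory results are listed with their grades. This safeguard is partial, because adverse event recording rests on a judgement of clinical relevance while the shift tables are graded by program.
- A reader might infer that the main safety conclusions are at risk. They are not. CRS is graded on fever, hypotension and hypoxia, and organ toxicities do not influence the grade. The DLT window opens with the first 116 or 152 mg dose. The hold rules count events. The ECG baseline is pre-dose, and vital signs are only listed.
- A routine CRS blood panel on Day 1 is not shown. Two days is longer than the dosing date, and Protocol 10.12.1 names a cytokine sample for suspected CRS, not repeat hematology or chemistry. Such draws are allowed, but the documents do not show that they are common.

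What the reply does not remove is that the stated rule gives the wrong baseline whenever such a draw exists, contrary to the SAP's own start of the on-treatment period and its ECG rule.

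**Conclusion.** The point holds for unscheduled or off-protocol laboratory samples drawn after the first dose on the same calendar day. For these, the SAP as written makes a post-dose value the baseline and removes it from the post-baseline data; where the value has worsened, the shift is understated. The liver-test categories and the exploratory liver and renal subgroups can also be wrong. Reading this as a threat to the overall primary CRS estimate, or as general concealment of acute toxicity, goes beyond the documents.

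Severity is minor to moderate. No count of affected participants can be given: the frequency of these draws is not documented, and any percentage of the 76 is an assumption that bounds exposed baselines only. The conclusion rests on a literal reading of the SAP and on sites following the pre-dose sampling rules for scheduled assessments.

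**What to change.** 1. In SAP 3.4 and 6.8.3, define laboratory baseline as the last non-missing value before the date and time of first dose.
2. Where time is missing on Day 1, take the scheduled C1D1 record as pre-dose and treat unscheduled Day 1 records as post-baseline. Align SAP 5.2.11 with this.
3. Amend the same-day sentence in SAP 3.5 so that post-dose Day 1 assessments are on-treatment.
4. Limit the worst-grade tie rule in SAP 6.8.3 to values known to be pre-dose. Taking the best grade instead is not a remedy, since it would bias shifts upward.

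The cost is SAP wording and one derivation rule. Dose time is recorded in the CRF (Protocol 6.4), and laboratory listings are already sorted by collection date and time (SAP 6.8.3), so no new data appear to be needed. The SAP is based on Protocol Amendment 2 while the protocol is at Amendment 4, so an aligning revision could carry the change. The downside is that a few same-day records without a time will follow a convention.
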